### 7.2 Statistical Methods

All statistical analyses will be performed under consultation with [name], Ph.D., a CTRC biostatistician. Our primary goal will be to assess changes in TRH stimulation test parameters at baseline compared to each thyroid hormone supplementation (LT4 or LT3) and our secondary goal will be to compare physiologic responses to LT4 and LT3 therapy from baseline. The area under the curve (AUC) for TRH-stimulated TSH response will be calculated using the trapezoidal rule. The maximum serum TSH concentration following TRH administration ( $TSH_{max}$ ) will be obtained by direct inspection of the serum concentration-time profiles. Changes in TSH bioactivity, free T4, and total T3 will be determined using the higher of the 120 or 180 minute post-TRH values. Paired t-tests will be used to examine change from baseline for each preparation, and two-tailed tests will be used to compare data between treatment arms. Nonparametric tests will be employed as needed. The primary outcomes will be the changes in TRH stimulation test parameters (AUC,  $TSH_{max}$ ,  $\Delta$  TSH bioactivity,  $\Delta$  free T4,  $\Delta$  total T3). Additional outcomes will include changes in unstimulated TSH bioactivity, REE, body temperature, weight, body composition, lipids, physical actigraphy and heart rate, cognitive testing, symptoms, arterial tonometry, and Doppler echocardiography.

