## ***1.2 Interventional Agents***

TRH, a naturally occurring hypothalamic neuropeptide in humans, is an endogenous ligand for the TRH receptor. It is composed of three amino acids and stimulates the release of TSH and prolactin from the anterior pituitary. The release of TSH then stimulates the release of thyroid hormones, T4 and T3 (Fig. 1). Synthetic TRH has been used for over 40 years in the diagnostic assessment of pituitary or hypothalamic dysfunction.

Intravenous TRH has a short half-life with a mean of approximately 5 minutes in normal subjects. Bassiri and Utiger administered 400 µg TRH to 8 healthy men and noted that plasma TRH levels rose from <0.4 ng/mL to  $33 \pm 7$  ng/mL (mean  $\pm$  SEM) 2 minutes after injection and linearly fell to 2.9 ng/mL 20 min after injection. The mean half-life of TRH was found to be  $5.3 \pm 0.5$  min.[10]. TSH levels rise rapidly; reach a peak, and later decline after TRH administration. Anderson *et al* administered 100-800 µg TRH to 79 healthy men and found that TRH-stimulated TSH levels peaked after 30 min and fell to baseline levels in approximately 3 hours.[11]

Levothyroxine (LT4) and liothyronine (LT3) are synthetic forms of T4 and T3, which are endogenous hormones produced by follicular cells of the thyroid gland in response to stimulation by TSH from the anterior pituitary. The majority of circulating thyroid hormone in the blood is in the form of T4. T4 is then converted to T3 in target tissues, with T3 being the more physiologically active hormone. Both T4 and T3 bind to the thyroid receptor in cell nuclei and regulate DNA transcription and protein synthesis. Human studies show that thyroid hormone levels can also alter TSH bioactivity. [4, 6, 12] T4 is metabolized slowly with eighty percent of circulating T3 derived from T4 through deiodination. The half-life of LT4 is six to eight days. The half-life of LT3 is one to two days.[13-15]

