#### LT3

The starting dose of liothyronine will be 1/3 of that of levothyroxine divided into three daily doses. We will titrate the dose according to subject weight and how far the TSH level is from goal. No dose adjustment will be greater than 8.3 mcg per day.

The total daily dose of study medications will be adjusted to a TSH of 0.5-1.5 mU/L using the adjustment scheme to avoid excess thyroid hormone replacement.

At the time of crossover of study drug, participants will undergo a 4 week wash-out period from the study drug. This is to avoid over-replacement when switching from LT4 to LT3, given the longer half-life of LT4. Following Visit 2, participants will stop all study drug for 4 weeks. At the end of 4 weeks they will begin the second study drug at the equivalent dose as they were taking at Visit 2, divided into 3 equal doses. TSH level will not be checked at the end of the wash-out period. A TSH level will be checked 4 weeks after crossing over to the new study drug. All further TSH level evaluations and medication adjustments will follow the titration protocol.

No direct benefits are expected to result from LT4 and LT3 administration.

The weight based dosing scheme and examples are displayed below:

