### **3 Study Design**

#### **3.1 General Design**

The study design is a randomized, double-blind, cross-over study in which we will examine the pituitary-thyroid axis in older subclinical hypothyroid individuals in response to TRH stimulation and to daily LT4 or LT3 supplementation over a minimum period of 14 consecutive weeks. Physiologic responses to LT4 and LT3 supplementation will also be examined. Thirty participants will receive a total of three TRH stimulation tests and one course each of LT4 and LT3 in randomized order.

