### **3.3 Secondary Study Endpoints**

The following endpoints will be measured at each study visit:

1. Unstimulated TSH bioactivity
2. Resting energy expenditure (REE) evaluation by indirect calorimetry
3. Weight
4. Body composition including body fat (percent and total), free fat mass, and bone density measured by dual energy x-ray absorptiometry (DXA)
5. Lipid profile via laboratory measurements
6. SF-36 for health status, hypothyroid symptoms (Appendix 2)
7. Heart rate and physical activity via actigraphy
8. Digit symbol substitution test
9. Body temperature using rectal temperature measurement
10. Optional exploratory genetic testing (one study visit only)
11. arterial tonometry, Doppler echocardiography, and arterial load assessment

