#### LT3

The starting dose of liothyronine will be 1/3 of that of levothyroxine ( 0.23 mcg/kg/day of LT3) divided into three daily doses. We will titrate the dose according to subject weight and how far the TSH level is from goal. No dose adjustment will be greater than 8.3 mcg per day.

CONFIDENTIAL

This material is the property of the University of Pennsylvania. Do not disclose or use except as authorized in writing by the study sponsor

The total daily dose of study medications will be adjusted to a TSH of 0.5-1.5 mU/L using the adjustment scheme to avoid excess thyroid hormone replacement.

At the time of crossover of study drug, participants will undergo a 4 week wash-out period from the study drug. This is to avoid over-replacement when switching from LT4 to LT3, given the longer half-life of LT4. Following Visit 2, participants will stop all study drug for 4 weeks. At the end of 4 weeks they will begin the second study drug at the equivalent dose as they were taking at Visit 2, divided into 3 equal doses. TSH level will not be checked at the end of the wash-out period. A TSH level will be checked 4 weeks after crossing over to the new study drug. All further TSH level evaluations and medication adjustments will follow the titration protocol.

No direct benefits are expected to result from LT4 and LT3 administration.

The weight based dosing scheme and examples are displayed below:

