## 7 Statistical Plan

### 7.1 Sample Size Determination

We plan to enroll 30 subjects with an anticipated 15% dropout rate. With an alpha of 0.05 and 80% power and 15% dropout, we will be able to detect a 0.58 standard deviation (SD) change in outcome from baseline. A 3 SD improvement in unstimulated TSH bioactivity has been reported after treatment of overt primary hypothyroidism.[4] No previous studies have measured TSH bioactivity in subclinical hypothyroidism.

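### The plan does not show or check that DXA outcomes and weight recover in the 4-week wash-out, yet 7.2 credits the whole Visit 1-to-Visit 3 change to the second drug; 3.1 also misstates exposure

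*Combined protocol and SAP*

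**What the plan says.** Sections 2 and 3.3 list weight, body composition and bone density as secondary outcomes, measured at each study visit (Visits 1, 2 and 3). Visit 1 precedes any thyroid preparation; Visits 2 and 3 take place on the first and second preparation.

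On the change-over, the LT3 text in 1.5 and 5.2 says: "At the time of crossover of study drug, participants will undergo a 4 week wash-out period from the study drug". The reason given is: "This is to avoid over-replacement when switching from LT4 to LT3, given the longer half-life of LT4". The same text says that TSH is not checked at the end of the wash-out, and no other outcome measurement is scheduled there.

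On analysis, 7.2 says: "Paired t-tests will be used to examine change from baseline for each preparation". Preparations are compared with each other by unspecified two-tailed tests. Period, sequence and carry-over are not mentioned. Bone density is not named in 7.2; it enters through the body-composition endpoint in 3.3 and the secondary objectives in section 2.

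On exposure, 3.1 describes "daily LT4 or LT3 supplementation over a minimum period of 14 consecutive weeks". Section 4.4.1 gives 14 to 78 weeks as the whole follow-up per participant.

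**The concern.** A wash-out set by drug half-life deals with circulating hormone. It does not show that a slowly changing outcome has returned to where it started. With a single baseline, a participant's second-drug change is Visit 3 minus Visit 1. Anything left over from the first drug, and any drift with time in people aged 70 and over, is booked to the second drug.

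The stated secondary objective is the change between baseline and each preparation. If carry-over is material, each preparation's estimate contains part of the other's effect, and the LT4-LT3 comparison is distorted. The exposure statement adds to this: a null DXA result would appear to rest on a longer unbroken exposure than the design guarantees.

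**Working it through.** **1. The plan's own figure.** Section 7.1 says "We plan to enroll 30 subjects with an anticipated 15% dropout rate" and, at alpha 0.05 and 80% power, "we will be able to detect a 0.58 standard deviation (SD) change in outcome from baseline". Completers: 30 × 0.85 = 25.5. A two-sided paired t-test (sidedness assumed) gives a detectable change of 0.584 SD at n = 25 and 0.572 SD at n = 26. The 0.58 SD reproduces, so the sample-size figure is not at fault.

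**2. Does the wash-out clear the drug?** Section 1.2 says: "The half-life of LT4 is six to eight days". LT4 remaining after 28 days is 0.5^(28/6) = 3.9% to 0.5^(28/8) = 8.8%. After at least 28 further days on the second drug it is 0.5^(56/6) = 0.16% to 0.5^(56/8) = 0.8%. LT3, with a half-life of one to two days, is below 0.01% after 28 days. The wash-out clears the drug. This says nothing about bone density, body composition or weight, for which the documents give no rate of return.

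**3. Carry-over in the pooled change.** Let t4 and t3 be the true effects and L the share of the first drug's effect still present at Visit 3. L is an assumption. Effects are taken to add, and sequences to be equal in size.

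- LT4 taken first shows t4; taken second it shows t4 + L·t3. The pooled LT4 change is t4 + L·t3/2.
- Likewise, the pooled LT3 change is t3 + L·t4/2.
- Their difference is (t4 - t3)(1 - L/2), which keeps 100%, 75% or 50% of its true size at L = 0, 0.5 or 1.
- If the drugs have different shares L4 and L3, the difference is t4(1 - L4/2) - t3(1 - L3/2). With equal effects t this equals t(L3 - L4)/2, a difference where none exists.

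**4. Effect on the test.** Suppose one drug moves an outcome by 0.58 SD and the other is inert, with n = 25 (13 taking the active drug first). The bias in the inert drug's pooled change is L × 0.58 × 13/25. Rejection rates of the nominal 5% test are from 40,000 simulated trials per row.

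| L | Bias (SD) | Rejection rate |
|---|---|---|
| 0 | 0 | 5% |
| 0.09 | 0.03 | 5% |
| 0.25 | 0.08 | 6.5% |
| 0.5 | 0.15 | 11% |
| 0.75 | 0.23 | 18% |
| 1 | 0.30 | 28% |

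The bias is proportional to the first drug's effect. If that effect were 0.10 SD (for illustration), the bias at L = 1 would be 0.10 × 13/25 = 0.05 SD.

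**5. Exposure.** Minimum total follow-up is 14 weeks (4.4.1), of which 4 are off drug (5.2). That leaves at most 14 - 4 = 10 weeks on drug, in two separate blocks. Fourteen weeks on drug across both preparations would need 14 + 4 = 18 weeks of follow-up; fourteen on each would need 14 + 4 + 14 = 32. Neither fits a 14-week minimum. One reconstruction that does uses section 6.4: a TSH at 4 weeks and 1 week of monitor wear in each period, so 4 + 1 + 4 + 4 + 1 = 14.

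**6. Cost of using the first period alone.** About 25.5/2 ≈ 13 participants per drug. The detectable change from baseline rises from 0.58 to about 0.85 SD, and the standard error is √2 ≈ 1.4 times larger. The LT4-LT3 comparison becomes between-subject, with a detectable difference of about 1.15 to 1.17 SD.

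**The case against.** A reader might infer that these outcomes cannot return to baseline in 4 weeks. The documents do not support that. They give no return rate for any of the three, and weight need not behave like bone. The case is most plausible for bone density, but it remains an assumption.

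The two parts of the point also pull against each other: if a short first period barely moves bone, there is little to carry over. That is right for the shortest periods. However, 6.4 allows TSH checks 4 to 8 weeks apart and a visit up to four weeks after the last TSH, and follow-up can reach 78 weeks, so first periods may be much longer.

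A reader might also infer that any LT4-LT3 difference is bound to shrink. That needs equal L for both drugs. Nor do the figures show that the first period alone should be the main analysis. With equal SDs, dropping the second period lowers the mean squared error of a from-baseline estimate only when L·t exceeds about 0.40 SD, since (L·t/2)² must exceed 1/12.75 - 1/25.5. First-period changes also have no untreated control, so elapsed time stays in them.

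Randomised order leaves about half of each drug's data free of carry-over. The factor 1/2 above already counts this; it reduces the bias without removing it.

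Finally, the phrase in 3.1 may be meant as the length of the study period, which would agree with 4.4.1. It would then be a wording fault, but supplementation would still be neither daily nor consecutive throughout.

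**Conclusion.** The point holds as a gap in the plan. Recovery of slow endpoints is neither shown nor checked, and the analysis assigns the full Visit 1-to-Visit 3 change to the second drug without modelling period, sequence or carry-over. The contamination of each drug's pooled change is L/2 of the other drug's effect. That is negligible if L or the first drug's effect is small, and up to 0.30 SD in the worked case at L = 1. These sizes rest on additive effects, near-equal sequences and an L that the documents do not give.

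The exposure conflict does not depend on L: at most 10 weeks on drug in two blocks fit inside the 14-week minimum. Five weeks per preparation is a reconstruction of the shortest path, not a figure in the protocol.

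The endpoints concerned are secondary. The primary outcomes are not affected by this point.

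**What to change.** In 7.2, for DXA outcomes (naming bone density) and weight:

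- Keep both periods in a mixed model with treatment, period and sequence and the Visit 1 value as covariate. This takes elapsed time and the carry-over common to both drugs out of the LT4-LT3 contrast. It cannot remove carry-over that differs between the drugs, because with two periods and no second baseline that is not separable from a sequence effect.
- For that reason, add a sensitivity analysis on Visit 1 to Visit 2 only. State its limits: about 13 participants per drug, a detectable change of about 0.85 SD, and a between-subject LT4-LT3 comparison.
- Present Visit 1-to-Visit 3 changes by sequence, labelled as the change after both preparations.

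Reconcile 3.1, 4.4.1, 5.2 and 6.4 so that the stated exposure matches the design, and interpret DXA results against each participant's actual exposure. How the schedule should read is for the sponsor to settle.

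The cost is protocol and SAP wording and a few extra tables. No visit, sample or change of treatment is needed. The sensitivity analysis will be imprecise and should be read as such.

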## Study Summary

Title	The Thyroid Axis in Older Individuals with Persistent Subclinical Hypothyroidism: a Mechanistic, Randomized, Double-Blind, Cross-Over Study of Levothyroxine (LT4) and Liothyronine (LT3) Administration
Short Title	LT4 and LT3 in Subclinical Hypothyroidism
Protocol Number	821564
Phase	
Methodology	Randomized, Double-Blind, Cross-Over Study
Study Duration	Three years
Study Center(s)	Single-center
Objectives	To examine the pituitary-thyroid axis in older individuals with persistent subclinical hypothyroidism utilizing dynamic testing with thyrotropin releasing hormone (TRH) stimulation under different therapeutic conditions of either LT4 or LT3. We will measure thyroid stimulating hormone (TSH) area under the curve (AUC), $TSH_{max}$ , change in TSH bioactivity, and change in free T4 and total T3 levels. All outcomes will be assessed at baseline and after achieving target TSH levels with each thyroid preparation.
Number of Subjects	Thirty
Diagnosis and Main Inclusion Criteria	Men and women aged 70 and older with persistent subclinical hypothyroidism
Study Dose, Regimen	Product, Route, 1. Intravenous TRH 200 µg at study visit 1 (baseline), study visit 2 (on first thyroid treatment), and study visit 3 (on second thyroid treatment) 2. Oral LT4 with a total starting dose of 0.7mcg/kg/day split into three daily doses and titrated to a target TSH level of 0.5 -1.5mU/L 3. Oral LT3 with a starting dose of 1/3 of the weight based LT4 dose divided into three daily doses titrated to a target TSH level of 0.5 -1.5mU/L
Duration administration	of 1. Three single administrations of TRH (at baseline study visit 1, study visit 2 on the first thyroid treatment, and study visit 3 on the second thyroid treatment) 2. LT4 taken as divided doses three times daily 3. LT3 taken as divided doses three times daily 4. For LT4 and LT3, there will be medication adjustments every four weeks as needed until the TSH level is at goal.

CONFIDENTIAL

This material is the property of the University of Pennsylvania. Do not disclose or use except as authorized in writing by the study sponsor

Reference therapy	None
Statistical Methodology	Changes in TRH stimulation test parameters and other outcomes will be compared from baseline for each thyroid hormone preparation (LT4 or LT3) via paired t-tests and between treatment arms via two-tailed tests. AUC for TRH stimulated TSH response will be calculated. Nonparametric tests will be employed as needed.

CONFIDENTIAL

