#### **LT4 and LT3:**

LT4 and LT3 have each been in therapeutic use for more than 50 years. Adverse reactions to either drug are exclusively related to excessive thyroid hormone, which can produce iatrogenic thyrotoxicosis. No serious adverse events were reported in a

CONFIDENTIAL

This material is the property of the University of Pennsylvania. Do not disclose or use except as authorized in writing by the study sponsor

published LT4/LT3 crossover study, and no symptoms of hyperthyroidism or hypothyroidism were reported.[25, 28] Participants will be asked about hyperthyroid symptoms, and a TSH level will be checked prior to the planned date if a patient reports any hyperthyroid symptoms.

Administration and monitoring of LT4 and LT3 will be modeled off of a published protocol.[28] The dosing of thyroid hormone will be based on published studies of thyroid hormone replacement in subclinical hypothyroidism. The literature supports a 1 mcg/kg/day dose for initiation of therapy.[29-34] We will tailor the thyroid hormone dose to each subject using a weight-based dosing scheme that is also based on how far the subject's TSH level is from goal. The dosing scheme is conservative. 1mcg/kg is the dose reported in the literature. The initial dose in our study will be lower than that - 0.7mcg/kg/day given that we are studying subjects 70 years and older. We will use thrice daily dosing due to the short half-life of LT3.

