### **6.4 Medication Titration (Q4Weeks)**

Participants will have TSH testing every 4 weeks (acceptable range 4-8 weeks) at a Penn outpatient laboratory facility until TSH is at goal, and then the participant will be scheduled for Visit 2. This visit can be scheduled up to four weeks from the date of the last TSH level.

Symptoms of palpitations and shortness of breath will be ascertained at the reminder calls prior to TSH level checks. The total daily dose of study medications will be adjusted by blinded study investigators to a TSH of 0.5-1.5 mU/L. New study medication for adjustment dosing will be mailed overnight to participants within 5 days of receipt of the interim lab results. Once the TSH is at goal, an activity and heart rate monitor will be mailed to the participant to wear one week prior to the next study visit.

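### The LT4 versus LT3 comparison is left to unnamed two-tailed tests with no period term, although the dosing rules of this two-period crossover may make time on drug differ by period

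*Combined protocol and SAP*

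**What the plan says.** Section 3.1 describes a randomised crossover with one course each of LT4 and LT3. For change from baseline, Section 7.2 names a test: "Paired t-tests will be used to examine change from baseline for each preparation". For the two drugs against each other it gives only sidedness: "two-tailed tests will be used to compare data between treatment arms", with nonparametric tests where needed. The Study Summary treats the TRH parameters and the remaining outcomes alike: "other outcomes will be compared from baseline for each thyroid hormone preparation (LT4 or LT3) via paired t-tests and between treatment arms", again with two-tailed tests and no model. Neither place mentions period, sequence or a crossover model.

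The dosing rules differ between periods:
- **Period 1** starts below the 1 mcg/kg/day that Section 1.5 takes from the literature: "The initial dose in our study will be lower than that - 0.7mcg/kg/day", or one third of that as LT3. It is then titrated.
- **Period 2** follows a 4-week washout, after which "they will begin the second study drug at the equivalent dose as they were taking at Visit 2" (Sections 1.5 and 5.2).
- **Length** is set by response. Under Section 6.4, TSH is checked every 4 weeks (4 to 8 accepted) "until TSH is at goal, and then the participant will be scheduled for Visit 2". For timing, "This visit can be scheduled up to four weeks from the date of the last TSH level". Section 6.5 repeats the procedure for the second drug.

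Section 5.3 randomises the order without stating a ratio or blocking.

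**The concern.** A participant who needs dose steps in period 1 may need none in period 2, because the second drug starts at a dose already matched to goal. Visit 2 would then follow a longer exposure than Visit 3. Weight, body composition, bone density and lipids are the outcomes most likely to depend on how long treatment has run.

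A period effect of this kind enters the LT4-LT3 difference with opposite sign in the two sequences. If the analysis ignores it, it inflates the error term. If completers are unequal by sequence, it also shifts the estimate. A period term is the usual remedy, and the plan does not provide for one. Because the test is unnamed, the choice among paired, unpaired and nonparametric tests is also left until after the data are seen.

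**Working it through.** **1. The plan's own figure.** Section 7.1: 30 enrolled, 15% dropout, alpha 0.05, 80% power, 0.58 SD. Completers: 30 × 0.85 = 25.5. A two-sided one-sample (paired) t-test with the noncentral t distribution gives a detectable change of 0.584 SD at n = 25, 0.578 at 25.5 and 0.572 at 26. The figure reproduces. It covers change from baseline only; no figure is given for LT4 versus LT3.

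**2. Time on drug.** With k dose steps, the at-goal TSH falls at 4(k+1) to 8(k+1) weeks. The visit comes about 1 week later at the earliest (the activity monitor is worn for the preceding week) and 4 weeks later at the latest.

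| Dose steps | At-goal TSH, weeks | Weeks on drug at the visit |
|---|---|---|
| 0 | 4-8 | 5-12 |
| 1 | 8-16 | 9-20 |
| 2 | 12-24 | 13-28 |

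These ranges leave out the up to 5 days allowed for mailing a new dose. Someone needing 1 mcg/kg/day requires (1.0 − 0.7)/0.25 = 1.2, so at least 2 upward steps. The at-goal TSH then comes at week 12 or later in period 1, against week 4 or later in period 2 if the 3:1 conversion holds. If the converted dose is too strong, the downward steps (0.08-0.09 mcg/kg/day, against 0.10-0.25 upward) could make period 2 the longer one. The number of steps is not known in advance, and the ranges overlap.

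**3. Effect on the LT4-LT3 comparison.** Let the within-person difference be τ + π in one sequence and τ − π in the other, with residual SD 1. Assumptions: π = 0, 0.25, 0.5 or 1.0 (the documents give no value), τ = 0.58 for illustration, 26 completers, two-sided 0.05.

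- Without a period term at 13:13, the expected variance is 1 + π² × 26/25. The interval is wider by √1.065 = 1.03, √1.26 = 1.12 and √2.04 = 1.43 for π = 0.25, 0.5 and 1.0.
- With a period term, the standard error is ½√(1/n₁ + 1/n₂): 0.196 at 13:13 and 0.202 at 16:10, whatever π is.
- Without a period term at 16:10, the shift is π(16 − 10)/26. With the term it is 0.

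Simulated results:

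| π (SD) | Power at 13:13, no term | Power at 13:13, with term | Type I error at 13:13, no term | Shift at 16:10, no term | Type I error at 16:10, no term |
|---|---|---|---|---|---|
| 0 | 81% | 81% | 5.0% | 0 | 5.0% |
| 0.25 | 79% | 81% | 4.3% | 0.06 | 5.2% |
| 0.5 | 74% | 81% | 2.9% | 0.12 | 5.7% |
| 1.0 | 51% | 81% | 0.6% | 0.23 | 5.5% |

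Under simple randomisation (an assumption), a split of 16:10 or worse among 26 has probability 33%.

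**4. Change from baseline.** Each drug's data pool first-period and second-period visits, so a period gap g adds ± g/2 around the mean change. For a true change of 0.58 SD at 13:13, power falls from 81% to 79% at g = 0.5 SD and to 74% at g = 1.0 SD.

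**5. A shift that differs by sequence.** Take differences of τ + 0.75 in one sequence and τ − 0.25 in the other, at 13:13. The estimate is off by (0.75 − 0.25)/2 = 0.25 SD with or without the period term. With τ = 0, type I error is 17% without the term and 23% with it, because the tighter interval surrounds the same biased estimate.

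**The case against.** The strongest case on the other side has four parts.

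- **The mechanism is inferred.** No section gives time to goal, a period effect, or how any outcome depends on weeks on drug. The 4-8 week TSH window adds up to 4 weeks of slack per check, as much as one dose step at 4-weekly checks. This stands. A reader might infer that period 1 will be the longer one; the rules make that plausible but do not establish it.
- **The design limits the harm.** Both on-treatment visits follow a TSH in the same 0.5-1.5 mU/L target, so the TRH parameters are measured at a similar thyroid state. This largely stands, and it is why the concern falls mainly on slow secondary outcomes.
- **The term does not match the mechanism.** Exposure may vary by person or by sequence. A common period term recovers only part of the first and none of the second, and in the example in step 5 it raises type I error. This stands as a limit on the remedy.
- **The text leaves room.** A biostatistician is consulted and nothing excludes a crossover analysis. That is true, but the plan still does not say which analysis will be done.

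A reader might also take the 14-week minimum in Section 3.1 as a floor for each preparation. That would need at least 14 + 4 + 14 = 32 weeks in all, whereas Section 4.4.1 puts the shortest follow-up at 14. The shortest path, 5 + 4 + 5 = 14 weeks, fits a total.

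**Conclusion.** The concern holds as a cheap improvement to a secondary comparison. The LT4-LT3 test is unspecified beyond sidedness, and the dosing rules give a specific reason to allow for period. Under the assumed period effects, omitting the term costs nothing at 0 SD, 2 points of power at 0.25 SD, 7 at 0.5 SD and 30 at 1.0 SD. At 16:10 it shifts the estimate by up to 0.23 SD. Every period-effect size here is an assumption.

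Two stronger readings are tempting. One is that the unadjusted comparison is invalid. The documents do not support that: order is randomised, a paired test without the term is conservative at equal sequences under a common period effect, and it keeps 5% error on average if sequences are allocated by coin flip. The other is that equal sequences guarantee an unbiased estimate. They do so only if the period shift is the same in both sequences. Nor are the change-from-baseline tests, the primary goal in Section 7.2, untouched: a period effect widens their error too, and the change proposed here leaves them as they are.

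**What to change.** In Section 7.2, with a matching line in the Study Summary, specify the LT4-LT3 comparison as a two-period crossover analysis. Either of these will do: a mixed model with treatment and period as fixed effects and participant as a random effect, or the equivalent two-sample t-test on within-person differences by sequence.

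Report weeks on drug by period and by sequence, from actual start and visit dates. A reader can then see whether exposure differed, and whether it differed by sequence, which the period term cannot correct. Any analysis by weeks on drug should be read as descriptive, because time to goal depends on response.

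The cost is text and one degree of freedom. With no period effect, power stays at 81% at 13:13 and falls from 81% to 79% at 16:10. No visit, dose or titration rule changes. The actual period-2 start date can be asked at a scheduled phone contact (Section 6.7).
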